## 1.5 Trial Feasibility

After obtaining the approval of ethics committee, a randomized controlled trial of cell salvage in cesarean section will be conducted at the Second Affiliated Hospital of Wenzhou Medical University. This pretest will help to adjust the protocol and operation, test the effectiveness of the data collection method, and the acceptability of the test design.

## 2 Objectives and Design

A randomized, controlled, single-blind and multi-centre clinical trial

### 2.1 Study Objects

#### 2.1.1 Primary Objective

- Blood loss of the subjects in 5 days post operation

#### 2.1.2 Secondary Objective

- PT/APTT, Hct and Hb in first and fifth day after surgery
- the number of units of donor blood transfused
- transfusion-related adverse reactions
- postoperative complications: amniotic fluid embolism, sepsis, acute respiratory distress syndrome, disseminated intravascular coagulation, wound infection, acute hemolysis, etc.
- mortality during hospital stay
- time to first mobilisation,
- duration of hospital stay
- intraoperative salvaged cell; before and after cesarean section, maternal's squamous epithelial cells, fetal red blood cells, serum potassium, free hemoglobin.
  - Before and after blood transfusion, maternal's electrolytes, PH value, fetal red blood cells, serum potassium, free hemoglobin
  - Total cost in hospital

Second Stage: Follow-up when pregnancy again:

- Neonatal hemolytic disease (Appendix 2)  
Determine blood type, antibody, and (Immunoglobulin G) IgG titer

### 2.2 Study Design

A randomized, controlled, single-blind and multi-centre clinical trial with cost-effective analysis.

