At the Second Affiliated Hospital of Wenzhou Medical University, we randomly invited 30 obstetricians to conduct a questionnaire survey. 29 of the surveys were successfully returned with a response rate of 96.7%. Data analysis shows that 89.66% of obstetricians were affected during their work due to blood difficulties. 89.66% of obstetricians have heard of intraoperative cell salvage, and 41.38% of obstetricians have used this technique in their work. 72.41% of obstetricians think autologous cell salvage is more beneficial than allogeneic blood transfusion, 27.59% of doctors are not sure which method is more favorable, but none of the doctors think that allogeneic cell salvage is more favorable than autologous blood recovery. Meanwhile, 100% of the doctors think it is necessary to have some research on the safety and efficacy of the two transfusion methods. When asking "if the mother needs blood transfusion during the cesarean section, are you willing to let the mother participate in this study", 48.28% of doctors are willing to, and 48.28% of doctors will be based on the condition. When asking the influence of postoperative bleeding according to the two transfusion methods, 68.97% of doctors are not sure about it. The above data not only show the good acceptance of autologous cell salvage from obstetricians, but also show the value of this trial.

At the Second Affiliated Hospital of Wenzhou Medical University, we randomly invited 30 anesthesiologists to conduct a questionnaire survey. All 30 of the surveys were successfully returned with a response rate of 100%. Data analysis shows that 76.67% of anesthesiologists were affected during their work due to blood difficulties. 26.67 % of anesthesiologists think autologous cell salvage is more beneficial than allogeneic blood transfusion, 66.67% of anesthesiologists are not sure which method is more favorable. The "uncertainty" is higher than obstetricians. Perhaps it is because anesthesiologists know more about intraoperative blood collection. When asking "if the mother needs blood transfusion during the cesarean section, are you willing to let the mother participate in this study", compared to obstetricians, there are also 48.28% of anesthesiologists would like to, and 48.28% of anesthesiologists will be based on the condition. When asking the influence of postoperative bleeding according to the two transfusion methods, compared to obstetricians, 68.97% of anesthesiologists are not sure about it.

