### 4.4 Randomization Process

Once subjects are confirmed through all the criteria and have received the informed

consent, they can be randomized to either the treatment group(Caesarean section with IOCS) or control group(Caesarean section without IOCS).The randomization will be proceed in operation if the patient needs blood transfusion.

Randomization (ratio:1:1) is used through a network-based randomization system, which follows SOP. We use central dynamic randomization system.

The randomization will be stratified by 5 conditions:

1. centers
2. type of cesarean section (Emergency/Elective)
3. whether there exist abnormality in placental
4. number of fetus (twins or more)
5. whether the ASA level is in I – II?

The randomization system will be tested and validated before the trial starts and will be supervised by the leader center's CRA and statistical expert throughout the trial. Once the subjects have been successfully grouped, they will be recorded in the enrollment form.

Each test center has their independent account and password for randomization system. The account number and password are authorized to the relevant staff by the major researchers in each center. After the staff has filled in the subject's ID and details into the randomization system, the system will display the grouping result.

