#### 4.5 Methods of Minimizing Risk and Bias

Using a third party to hide the grouping will help reduce the errors caused by selection. The randomization will be proceed in operation, and the staff should set blinding to the subjects.

Operational errors could result in change in blood transfusion rate. To minimize this risk, we need to make sure that all operating rooms and recovery wards in each center use an unified blood transfusion plan. Each medical team within each center should have same start-up criterion for setting up blood transfusion. Before participating in the trial, each center should provide a blood transfusion plan to the leader center for record. Some centers would use a prespecified value of Hb to determine whether blood transfusion is needed and this value should be unified among each center's medical team. If any of the following symptoms presents, such as unconscious, dyspnoea, exhaustion, which could clearly indicate level of red cell, blood transfusion is needed. Maternal mobility and neonatal care after cesarean section are different from the postoperation rehabilitation activity of most bedridden patients. According to the practical issues, since the clinicians may have different point of view, it is allowed to have little variation between each center. It represents the difference in reality cross the clinic, so it will not increase the bias.

Postpartum ward medical staff should use an unified blood transfusion plan as far as possible, according to the postoperative Hb levels and maternal symptoms. Do not deliberately observe the grouping of subjects.

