## 4.9 Relevant Operating Plan

### 4.9.1 Assessment Method for Intraoperative and Postoperative haemorrhage in Obstetrics

- Assessment Method for Intraoperative blood loss in Cesarean Section
  - ❖ Weighing Method: blood loss (ml)  $\approx$  (weight of gauze with blood – weight of dry gauze) /1.05
  - ❖ Measuring Cup Method: used to measure amount of blood in a curved plate; blood loss ml=Volume of measuring cup (blood clots crush as much as possible).
  - Intraoperative blood loss = Recycling machine blood volume (recovery machine capacity - flushing, washing capacity) + Placental bleeding (using measuring cup to measure the amount of blood flow into the curved plate by

- squeezing the placenta) + blood volume of cleaning the vagina (bleeding with weighing method, blood clots with measuring cup method) + blood volume of gauze (bleeding with weighing method, blood clots with measuring cup method)
- Postoperative blood loss = blood volume of postpartum sterile mattress + blood volume of gauze (bleeding with weighing method, blood clots with measuring cup method) + volume of shed blood (using measuring cup)

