### **7.2.2 Causal Analysis**

Investigators must assess the causal relationship between all adverse events and the trial.

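### Only the woman is blinded, and an instruction to ward staff is the sole protection for assessor-dependent postoperative outcomes; laboratory Hct/Hb is much less exposed

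*Combined protocol and SAP*

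**What the plan says.** - **Level of blinding.** Section 2.2 describes "A randomized, controlled, single-blind and multi-centre clinical trial with cost-effective analysis"; Table 1 and the opening of section 2 also say single-blind. Section 4.5 names the blinded party: "the staff should set blinding to the subjects".
- **Who sees the arm.** In section 4.4, authorised staff at each centre enter the woman's details and "the system will display the grouping result". Section 4.5 places randomisation during the operation.
- **Ward safeguard.** Section 4.5 asks postpartum staff to follow one transfusion plan as far as they can, and adds: "Do not deliberately observe the grouping of subjects". No procedure supports this.
- **Primary outcome.** Section 2.1.1 gives "Blood loss of the subjects in 5 days post operation". Section 8.2.1 says direct measurement is difficult and uses day-1 and day-5 Hb and Hct to reflect the loss. Section 8.1.1 has a formula from the fall in Hct plus transfused red-cell volume (Vt). Section 4.9.1 separately defines postoperative loss from mattress, gauze and shed blood, by weighing and by cup: "Volume of measuring cup (blood clots crush as much as possible".
- **Other outcomes.** Section 2.1.2 lists donor units, transfusion reactions, complications, mobilisation and length of stay. Section 7.2.2 adds: "Investigators must assess the causal relationship between all adverse events and the trial".
- **Staff opinion.** Section 1.4 reports that "72.41% of obstetricians think autologous cell salvage is more beneficial than allogeneic blood transfusion" and that none favour donor blood. It also reports that 68.97% of the obstetricians are unsure about the effect on postoperative bleeding, and that 66.67% of anaesthesiologists are unsure which method is better.

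**The concern.** Randomisation makes the groups comparable at allocation. It does not stop a later measurement or decision from being influenced by knowledge of the arm. Several outcomes here leave room for that: how thoroughly clots are measured, whether a fever is called a transfusion reaction, when a woman is mobilised or discharged, and whether a unit is given when the plan leaves it to staff opinion. If those who decide know the arm and expect salvage to do better, the differences can tilt towards salvage with no true effect. A larger sample would not remove the tilt. Assessors on the ward are a separate group that could often be kept unaware, even though the theatre team cannot be.

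**Working it through.** **Step 1. Who is protected from knowing the arm.** The woman is blinded by procedure (4.5) and ward staff have an instruction only (4.5). The theatre team cannot be blinded, since it runs the salvage machine (Appendix 3). For adverse-event assessors no masking is stated (7.2.2). Laboratory samples carry the study number (6.2), which is most of what is needed. For the statistician, section 9.3 locks the data before analysis but does not say that the arms are coded. The committee in section 9.4 audits data analysis, which does not mask outcome assessment.

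**Step 2. Outcomes side by side.**

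| Outcome | Section | How staff can influence it | Exposure |
|---|---|---|---|
| Weighed and cup-measured loss | 4.9.1 | Technique and completeness | High if the measurer knows the arm |
| Reactions, complications | 2.1.2, 4.8 | Recognition and labelling | High |
| Adverse-event causality | 7.2.2 | Investigator opinion | High |
| Mobilisation, length of stay | 2.1.2 | No criteria stated | Moderate to high |
| Postoperative donor units | 2.1.2, 4.5, 4.7 | Discretion between 70 and 100 g/L | Moderate |
| Laboratory Hct/Hb, days 1 and 5 | 8.2.1 | Little, apart from earlier transfusion | Low |

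The exposure grades are my assessment; the plan gives none.

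**Step 3. How knowledge of the arm could reach the calculated loss.** The formula in section 8.1.1 is loss = BV × (Hct day 1 − Hct day x) + Vt.

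- Inputs: one unit is about 200 ml (4.7, donor group example). BV = 100 ml/kg × 60 kg = 6000 ml (4.7, formula and example weight).
- Assumptions: the unit is given between the two Hct samples, it counts in Vt, and BV is held fixed.
- One extra discretionary unit changes the calculated loss by 200 − 6000 × (rise in Hct).
- With no rise in Hct the change is +200 ml. With a rise of 200/6000 = 0.033 it is 0.

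So a discretionary unit moves the calculated loss by between 0 and 200 ml over that range. The documents give no Hct response per unit and no rate of discretionary units by arm. The net shift therefore cannot be sized. It is at least partly self-correcting whenever Hct rises.

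**Step 4. What the survey supports.**

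- Obstetricians at one centre, 29 returns: 21/29 = 72.41% rate salvage more beneficial (exact 95% interval 53% to 87%), 8/29 = 27.59% are unsure, none favour donor blood. On postoperative bleeding, 20/29 = 68.97% are unsure.
- Anaesthesiologists, 30 returns: 8/30 = 26.67% favour salvage, 20/30 = 66.67% are unsure.
- The 68.97% also printed for anaesthesiologists on postoperative bleeding equals 20/29 and cannot arise from 30 returns (20/30 = 66.67%, 21/30 = 70.00%), so I do not use it.

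The figures reproduce. They show a general preference among obstetricians, but not a shared expectation about bleeding. Ward nurses were not among the groups surveyed.

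**The case against.** The strongest reply is that the primary outcome is a laboratory value. Section 8.2.1 chooses Hb and Hct because direct measurement is difficult, and section 4.9.1 never calls its method the primary endpoint. This stands, and it confines the point mainly to other outcomes. It does not close the matter, because the plan never says which route supplies the blood-loss volume tested in section 8.3.3.

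A reader might infer that staff who know the arm measure the five-day loss. The documents do not say so. They do not name the measurer, and they tell ward staff not to look for the group. Nor do they provide anything that would keep the group from them.

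A reader might also combine the pilot mean of 444 ml and SD of 709 ml with an assumed percentage under-reading in the salvage arm and derive an inflated rate of false superiority. The documents do not support this. Those pilot figures come from the Hct formula, not from pads and cups; the under-reading has no source; and section 8.3.3 names log-rank and Cox methods rather than a comparison of means.

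It can also be said that samples already carry study numbers and that data are locked before analysis. The first largely covers the laboratory. The second prevents later edits but does not stop the analyst from choosing a method with the arms in view, and section 8.3.1 leaves ANOVA or Wilcoxon open. Finally, postoperative transfusion and reactions are recorded on the ward (4.8), so exposure may be visible there. That limits what masking can achieve.

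**Conclusion.** The point holds for outcomes that depend on staff: directly measured postoperative loss, reactions and complications, adverse-event causality, mobilisation, length of stay, and discretionary postoperative transfusion, which feeds both donor units and Vt. For these the plan has an instruction but no procedure. It holds only weakly for laboratory Hct/Hb. No size can be given from the documents, and no false-positive rate for the primary outcome should be quoted while the source of the tested volume is unstated. The survey should be cited with both sides: a preference among 29 obstetricians at one centre, with most of them unsure about bleeding and most anaesthesiologists unsure overall. It does not show that staff in general are partial. The conclusion rests on the text available; the committee subsections listed under section 10 could not be read, so nothing is inferred from them. The change should be made because it is cheap, but the gap does not by itself invalidate the primary comparison.

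**What to change.** In sections 2.2 and 4.5, state that the woman and, where feasible, the postoperative assessors are masked, using existing staff:

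1. Keep the allocation off the ward blood-loss and outcome sheets. It stays available at once when care needs it, and each unmasking is logged.
2. Have ward staff who were not in theatre measure postoperative loss and record mobilisation.
3. Label maternal samples by study number and time point only; section 6.2 already uses study numbers.
4. Keep the arms coded for the statistician until the primary analysis is fixed, including the choice between ANOVA and Wilcoxon in section 8.3.1.
5. Add arm-masked review of reactions and complications only if the existing committee's remit allows it without extra staff. Otherwise, report that these were assessed with possible knowledge of the arm.

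The cost of items 1 to 4 is protocol wording, a change to the ward forms and an unmasking log, with no new posts. The downside is that masking will be incomplete, because transfusion exposure may be visible on the ward. Unmasking should therefore be reported by arm.

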### 3 Subjects Screening

Subjects: Woman who are admitted to a participating labor ward who fulfil all the following criteria will be eligible to be randomized.

#### 3.1 Eligible Criteria

##### 3.1.1 Inclusion Criteria

- 18 years of age or elder
- admitted to a participating labor ward
- delivery by elective or emergency caesarean section with an identifiable increased risk of haemorrhage
- ability to provide informed consent
- needing for blood transfusion during CS (according to blood transfusion guidelines [Appendix 1], obstetrician or anesthesiologist's advice)

### 3.2 Midway-Withdraw of Subjects

After completing randomization, the subjects will be considered as midway-withdraw from the study if:

[figure not shown]
- does not meet the inclusion criteria;
- for safety issue, one of the transfusion methods must be applied;
- subjects is no longer able to agree to participate the trial;
- subjects withdraw their consent form during the trial or during data collection;
- subjects no longer need cesarean section.

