### 3.3 Data Collection and Follow-up for Midway-Withdraw Subjects

If the investigator or the clinician or medical team providing the medical service believes that the subject needs to withdraw from the trial, it must be accepted from the medical point of view. It is the participants' freedom to determine whether continue follow-up after surgery or not. However, it is unavoidable that those midway-withdraw subjects will lead to biased outcome and the efficacy of the clinical trials will be worsen. Investigators need to collect and record the reasons and adverse events to any violation of the protocol as far as possible. The follow-up of maternal is also needed for safety issues. Maternal is still free to quit the program after completing the randomization. We will have to keep a record for the quit. Meanwhile, whether maternal agrees to be followed is also necessary to be recorded, if the participant decides to withdraw the study. If the subject explicitly requests to return all the data records, their decisions should be respected and be recorded to the final study form. When maternal is unable to obtain the informed consent during the trial, it turns to her legal representative's decision of whether continue or not.

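### Section 3.2 makes loss of the ability to agree after randomisation a withdrawal criterion in itself, 3.3 leaves the case to the legal representative, and outcome-related data loss can follow

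*Combined protocol and SAP*

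**What the plan says.** Section 3.2 opens its list with "After completing randomization, the subjects will be considered as midway-withdraw from the study if". One item is "subjects is no longer able to agree to participate the trial". It carries no exception and gives no role to a representative. A separate item in the same list reads "subjects withdraw their consent form during the trial or during data collection".

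Section 3.3, on data collection and follow-up for withdrawn women, ends: "When maternal is unable to obtain the informed consent during the trial, it turns to her legal representative's decision of whether continue or not". The same section says that "it is unavoidable that those midway-withdraw subjects will lead to biased outcome". It asks for reasons and adverse events to be recorded as far as possible and adds: "The follow-up of maternal is also needed for safety issues". Otherwise it leaves follow-up after surgery to the woman's choice.

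Written consent is required before surgery, and oral or retrospective consent is refused (4.2.2, 4.3). On timing, 4.4 says: "The randomization will be proceed in operation if the patient needs blood transfusion". Section 8.2.1 bases the primary outcome on Hb and Hct on days 1 and 5. Table 1 names a FAS, a per-protocol set and a safety dataset. Section 8.3.4 does not say how withdrawn women are analysed.

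**The concern.** Two sections deal with a woman who can no longer speak for herself, and they do not say the same thing. Under 3.2 incapacity is enough to class her as withdrawn. Under the last sentence of 3.3 someone else decides whether she continues. A centre working from 3.2 may stop collecting her data, while a centre working from 3.3 may approach the representative and keep her.

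Incapacity is not a neutral reason for loss in this population. Complications listed as outcomes in 2.1.2, such as amniotic fluid embolism, sepsis, acute respiratory distress syndrome and disseminated intravascular coagulation, can plausibly take away capacity, and so can severe bleeding. If such women leave after randomisation, and more often in one arm than the other, those who remain are no longer a fully randomised comparison on a strongly skewed outcome.

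**Working it through.** **1. The two rules side by side.**

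| | 3.2 | 3.3, last sentence |
|---|---|---|
| Event | no longer able to agree, after randomisation | unable to give consent during the trial |
| Consequence | classed as withdrawn | representative decides on continuing |
| Exception | none stated | not applicable |
| Reference to the other section | none | none |

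Because 3.2 lists withdrawn consent separately, the item on ability is most naturally read as incapacity and not refusal. No other section settles the case.

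**2. Which women are affected.** The 3.2 list applies only after randomisation. Under 4.4 that is during the operation, once transfusion is needed. (Section 4.3 places randomisation at preparation; I follow 4.4, with which 4.5 agrees.) The women concerned are therefore those who lose capacity later in the operation or afterwards. Each has already given written consent.

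**3. What is kept once a woman is classed as withdrawn.** Section 3.3 asks for the reason, adverse events and safety follow-up. It does not require day 1 and day 5 Hb/Hct. The FAS is not defined, so nothing states that she stays in it.

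**4. The plan's allowance for losses.** Section 8.1.1 uses n = (t × s / δ)² with t = 1.96, s = 709 and δ = 200:

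(1.96 × 709 / 200)² = 48.28, rounded up to 49; the plan states 50.

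50 × 1.2 = 60 per arm, 120 in total, as stated. This allows for 10 of 60 women per arm (16.7%). It replaces lost numbers; it does not correct for selective loss.

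**5. Illustration of sensitivity.** Inputs from the pilot table in 8.1.1: N = 48, mean 444, SD 709, maximum 4347. Suppose that the one woman lost is the heaviest bleeder.

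- New mean: (48 × 444 − 4347) / 47 = 16965 / 47 = 361 ml.
- Shift: 444 − 361 = 83 ml.
- New SD: √{[47 × 709² + 48 × 444² − 4347² − 47 × 360.96²] / 46} ≈ 419, down from 709.
- In an arm of 60 with the same mean and one such woman, the shift is (4347 − 444) / 59 = 66 ml.

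This shows how far a single loss from the tail can move a mean. It does not estimate the bias in this trial, because the documents give no rate of incapacity, overall or by arm.

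**The case against.** Five stronger readings are tempting, and the documents do not support them.

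- **A centre cannot comply with both sections.** Section 3.3 is headed as dealing with women already withdrawn. Its last sentence could mean only that the representative decides about follow-up, and on that reading a centre can follow both. The wording is not limited to follow-up, so the text is ambiguous and not flatly contradictory. Even on the milder reading, 3.2 still withdraws every woman who loses capacity, so the risk of selective loss remains.
- **These women are removed from the analysis and the safety comparison.** Nothing says so. Section 3.3 still asks for adverse events and safety follow-up. The gap is that nothing says they are kept in the FAS or that their Hb/Hct is still collected.
- **The unconsciousness in 4.5 triggers withdrawal.** Section 4.5 says that with symptoms "such as unconscious, dyspnoea, exhaustion, which could clearly indicate level of red cell, blood transfusion is needed". Unconsciousness that prompts the first transfusion precedes randomisation under 4.4, so 3.2 does not reach it. Only later incapacity counts.
- **A general anaesthetic given after signing would count.** This is strained; nothing suggests that centres would apply 3.2 to routine anaesthesia.
- **The 83 ml is the expected bias, and a large share of the 200 ml in 8.1.1.** The 200 ml is the half-width in a one-sample precision formula, not a treatment effect. The figure assumes that the 4347 ml woman lost capacity, which the documents do not say, and that the loss falls in one arm; similar losses in both arms would largely cancel. The pilot formula counts loss after the first postoperative day plus transfused red-cell volume, so collapse during surgery need not mean a high value. Section 8.3.3 judges by a log-rank test and the median, and removing one maximum from 48 values barely moves a median.

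These limits remove any claim about size. They leave the unreconciled wording and the unstated handling of the data.

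**Conclusion.** The point holds as a gap in the rules with a plausible route to bias. Section 3.2 makes incapacity after randomisation a withdrawal criterion in itself; 3.3 appears to leave the same case to the representative; and centres could act differently. The link to outcome is an inference: incapacity at that stage plausibly goes with severe bleeding or complications, and 3.3 itself accepts that withdrawals bias the result.

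The size cannot be computed, because no rate of incapacity is given. The move from 444 to 361 ml is a one-arm worst case on the mean. It assumes that the woman lost is the most extreme of 48. The conclusion rests on the wording and does not depend on that figure. It is worth acting on because a small amendment removes the risk.

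**What to change.** Reconcile 3.2 and 3.3 as follows.

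1. State that incapacity arising after valid written consent is not by itself a withdrawal criterion, and that the representative's decision described in 3.3 governs.
2. State that, unless the woman or her representative declines, routine in-hospital outcome data continue to be collected: day 1 and day 5 Hb/Hct, transfusions and adverse events.
3. State that she is analysed in the FAS in her randomised arm.

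This governs data collection and analysis only. It says nothing about her treatment, which stays with the clinical team.

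The cost is a wording amendment. The data items are already in the schedule in 4.8 or the outcome lists in 8.2, so no visits are added. The small downside is that a representative may have to be approached, and the ethics committee must confirm the consent wording.
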